6.4.2. Pharmacokinetic Drug Assays

Blood samples for determination of verinurad, M1, M8, allopurinol and oxypurinol concentrations in plasma will be analysed by Covance Bioanalytical Services on behalf of AstraZeneca, using validated assays.

Full details of the analytical method and analyses performed will be described in a separate bioanalytical report.

Exploratory blood samples for cyclosporine and rifampicin will be stored by Covance Bioanalytical Services on behalf of AstraZeneca until the decision for analysis is made. Full details of the analytical method and analyses performed will be described separately to this document.

6.5. Pharmacodynamics

This section is not applicable as there are no pharmacodynamic assessments in this study.

6.6. Pharmacogenetics

This section is not applicable as there are no pharmacodynamic assessments in this study.

6.7. Biomarkers

This section is not applicable as there are no biomarker assessments in this study.

6.8. Immunogenicity

This section is not applicable as there are no immunogenicity assessments in this study.

6.9. Metabolites

No additional blood samples will be collected for metabolite identification.

7. BIOLOGICAL SAMPLES PROCEDURES

All biological samples will be collections will be performed by trained staff and in accordance with the Clinical Unit's SOPs.

7.1. Total Blood Volume

The approximate total amount of blood to be collected from each subject in this study, excluding repeat samples, is summarised in Table 7-1.

Table 7-1 Total Blood Volume

	Volume per Sample	Number of Samples	Total
Haematology	2.7 mL	7	18.9 mL
Clinical chemistry ^a	7.5 mL	4	30.0 mL
	2.6 mL	3	7.8 mL
HLA-B*58:01 allele genotyping	3.0 mL	1	3.0 mL
SARS-CoV-2 antibody ELISA	2.6 mL	1	2.6 mL
PK blood draws for verinurad and metabolites	3.0 mL	51	153.0 mL
PK blood draws for allopurinol	2.0 mL	51	102.0 mL

	Volume per Sample	Number of Samples	Total
Exploratory PK blood draws for cyclosporine	1.0 mL	17	17.0 mL
Exploratory PK blood draws for rifampicin	1.0 mL	17	17.0 mL
Total			351.3 mL

ELISA: Enzyme-linked immunosorbent assay; HLA-B: Human leukocyte antigen B; FSH: Follicle-stimulating hormone.

Repeat blood samples may be collected for safety reasons. The maximum volume to be drawn from each subject must not exceed 500 mL.

7.2. Handling, Storage and Destruction of Biological Samples

Samples will be disposed of, on instruction from AstraZeneca, after the CSR has been finalised, unless samples are retained for additional or future analyses.

7.2.1. Pharmacokinetic Samples

Pharmacokinetic samples will be disposed of after the bioanalytical report finalization or 6 months after issuance of the draft bioanalytical report (whichever is earlier), unless requested for future analyses.

Pharmacokinetic samples may be disposed of or anonymized by pooling. Additional analyses may be conducted on the anonymized, pooled PK samples to further evaluate and validate the analytical method. Any results from such analyses may be reported separately from the CSR.

Incurred sample reproducibility analysis or additional assay development work, if any, will be performed alongside the bioanalysis of the test samples. The results from the evaluation, if performed, will be reported in a separate Bioanalytical Report.

7.2.2. Pharmacodynamic Samples – Not Applicable

7.2.3. Pharmacogenetic Samples – Not Applicable

7.3. Labeling and Shipment of Biohazard Samples

Samples will be labeled and shipped in accordance with the Laboratory Manual and the Biological Substance, Category B regulations (materials containing or suspected to contain infectious substances that do not meet Category A criteria), see Appendix B of this CSP 'IATA 6.2 Guidance Document'.

^a When applicable, serology and FSH (females only) analyses will be performed on the sample collected for clinical chemistry analyses.

Any samples identified as Infectious Category A materials will not be shipped and no further samples will be taken from the subject unless agreed with AstraZeneca and appropriate labeling, shipment and containment provisions are approved.

7.4. Chain of Custody of Biological Samples

A full chain of custody will be maintained for all samples throughout their lifecycle.

The Investigator will ensure full traceability of collected biological samples from the subjects while in storage at the centre until shipment and will keep documentation of receipt of arrival.

The sample receiver will keep full traceability of samples while in storage and during use, until used, disposed of, or until further shipment or disposal (where appropriate) and will keep documentation of receipt of arrival.

Samples retained for further use will be registered in the AstraZeneca biobank system during the entire life cycle.

7.5. Withdrawal of Informed Consent for Donated Biological Samples

If a subject withdraws consent to the use of donated biological samples, the samples will be disposed if not already analysed and the action documented.

As collection of donated biological samples is an integral part of the study then the subject is withdrawn from further study participation.

AstraZeneca ensures the central laboratory(ies) holding the samples is/are informed about the withdrawn consent immediately and that samples are disposed of/destroyed, the action documented and the signed document returned to the Clinical Unit.

8. ETHICAL AND REGULATORY REQUIREMENTS

8.1. Ethical Conduct of the Study

The study will be performed in accordance with ethical principles that have their origin in the Declaration of Helsinki (version 1996) and are consistent with ICH GCP and the AstraZeneca policy on Bioethics and Human Biological Samples.

8.2. Subject Data Protection

The ICF will incorporate (or, in some cases, be accompanied by a separate document incorporating) wording that complies with relevant data protection and privacy legislation.

All clinical study findings and documents will be regarded as confidential. The Investigator and members of his/her research team must not disclose such information without prior written approval from the Sponsor.

The anonymity of participating subjects must be maintained. Subjects will be specified in outputs and other documents containing subject data by their subject number, not by name. Documents that identify the subject (eg, signed ICF) will be maintained in confidence by the Investigator.

Study data will be stored in accordance with local and global data protection laws.

8.3. Ethics and Regulatory Review

The study will be submitted to the national regulatory agency (Federal Institute for Drugs and Medical Devices [BfArM]) for review and approval, by Parexel in accordance with local regulatory procedures.

The study will be submitted to the IEC for ethical review and approval by the Investigator in accordance with local procedures.

Parexel will provide the IEC and Investigator with safety updates/reports according to local requirements, including SUSARs, where relevant.

AstraZeneca will provide the regulatory authority with safety updates/reports according to local requirements, including SUSARs, where relevant.

Compensation will be reasonable and related to the nature and degree of inconvenience and discomfort as a result of participation in the study. Information on how participants will be compensated is contained in the ICF.

8.4. Insurance

The Sponsor has covered this clinical study by means of an insurance of the clinical study according to national requirements. The name and address of the relevant insurance company, the certificate of insurance, the policy number and the sum insured are provided in the Investigator's Site File.

8.5. Informed Consent

The subjects shall be informed of the nature, significance, implications and risks of the trial, and ICF will be freely given and evidenced in writing, dated and signed, or otherwise marked, by the subject as evidence to indicate his/her free ICF, prior to the start of the study.

The nature of the ICF will comply with the Declaration of Helsinki (version 1996), the current requirements of GCP (CPMP/ICH/135/95) and local regulation which ever offers the greater subject protection.

8.6. Changes to the Protocol and Informed Consent Form

Study procedures will not be changed without the mutual agreement of the Investigator and AstraZeneca.

If there are any substantial changes to the study protocol, then these changes will be documented in a study protocol amendment and where required in a new version of the study protocol.

If a protocol amendment requires a change to the ICF the IEC should approve the revised ICF before the revised form is used.

If local regulations require, any administrative change will be communicated to or approved by the IEC.

9. DATA QUALITY ASSURANCE AND DATA MANAGEMENT

9.1. Quality Control and Source Data Verification

Source data verification will be conducted with due regard to subject confidentiality.

The Clinical Unit will allow the study monitor and Sponsor representative direct access to all study documents, medical files and source documents to enable verification of the study data, while maintaining the anonymity of the subject and confidentiality of the data.

Internal quality control will be performed at all stages of the study by the Clinical Unit.

9.2. Audit/Inspections

The Clinical Unit facilities and all study data/documentation may be audited/inspected by independent auditor/inspector/any representatives of regulatory authorities. The Investigator must allow the applicable persons access to all relevant facilities and data/documents. The Investigator must be available to discuss any findings/issues.

If an audit was performed, the audit certificate will be included in the CSR.

9.3. Study Monitoring

The conduct of the study will be monitored by an independent Parexel monitor to ensure compliance with applicable regulatory requirements and GCP. The summary of the documentation of the monitoring visits will form part of the study documentation and will be archived as such.

Monitoring visits at site will be limited to a minimum required as deemed appropriate during COVID-19 pandemic.

9.4. Data Collection

The ClinBaseTM system is an electronic source data capturing and information management system. The system combines all aspects of source data capturing with process control and clinical study management. All clinical and laboratory data, except those which are paper-based or provided by external vendor, will be collected in ClinBaseTM. Only paper-based data will be subject to data entry. For electronic source data, no data entry will be performed.

The responsible study monitor will check data at the monitoring visits to the Clinical Unit. The Investigator will ensure that the data collected are accurate, complete and legible. Data will be monitored within ClinBaseTM by the study monitor before being exported. Any changes made during monitoring will be documented with a full audit trail within ClinBaseTM.

9.4.1. Case Report Forms and Source Documents

All data obtained using paper collection methods during the clinical study will be recorded in ClinBaseTM. All source documents from which ClinBaseTM entries are derived should be placed in the subject's personal records.

The original ClinBaseTM entries for each subject will be checked against source documents by the study monitor. Instances of missing or uninterpretable data will be discussed with the Investigator for resolution.

9.4.2. Access to Source Documents

During the course of the clinical study, a study monitor will make Clinical Unit visits to review protocol compliance, compare ClinBaseTM entries and individual subject's personal records, assess IMP accountability and ensure that the clinical study is being conducted according to pertinent regulatory requirements. ClinBaseTM entries will be verified against source documents. The review of medical records will be handled confidentially to ensure subject anonymity.

Checking of the ClinBase[™] entries for completeness and clarity and verifying with source documents, will be required to monitor the clinical study for compliance with GCP and other regulations. Moreover, regulatory authorities of certain countries, IECs may wish to carry out source data inspections on-site, and the Sponsor's clinical quality assurance group may wish to carry out audits. Direct access to source data will be required for these inspections and audits; they will be carried out giving due consideration to data protection and subject confidentiality. The Investigator assures the Sponsor of the necessary support at all times.

9.5. Data Management

Parexel will utilize standardized and validated procedures and systems to collect, process and file the clinical data of this study. Any system used will be compliant with FDA 21 Code of Federal Regulations Part 11 requirements.

A DMP will be prepared to describe the processes and data-flow within the clinical study. Timelines, versions for the computer systems and the coding will be defined in the DMP, and if applicable, Sponsor specific requests will also be documented within. The DMP will be finalised before first dose where possible but before database lock.

A DVS will be created to outline the validation checks to be performed during the study. The DVS must be finalised before data validation.

After the data has been monitored by the responsible study monitor all data received will be reviewed, logged and filed.

The raw data intended for further processing will be checked by standard routines or according to the DVS and queries will be generated and sent to the Investigator for review and resolution. Corrections resulting from these queries will be confirmed on the DCFs. This process will be repeated until no further discrepancies are found. The data will then be declared as clean. Applicable documentation will be stored in the study files.

Only trained study staff will have access to the clinical database and every change in data will have a full audit trail.

10. EVALUATION AND CALCULATION OF VARIABLES

10.1. Safety Variables

10.1.1. Adverse Events

All AEs will be coded using the latest version of the MedDRA vocabulary, and will be listed for each subject.

Adverse events will be assigned to a treatment based on the start date/time of the AE in relation to dosing in that treatment period; for tabulation purposes the AE will then be assigned to the treatment received in the respective treatment period as follows:

- Treatment Period 1: AEs with start date/time at the time of or after dosing in Treatment Period 1 until the time of dosing in Treatment Period 2.
- Treatment Period 2: AEs with start date/time at the time of or after dosing in Treatment Period 2 until the time of dosing in Treatment Period 3.
- Treatment Period 3: AEs with start date/time at the time of or after dosing in Treatment Period 3 until the Follow-up Visit,

Adverse events with missing start dates/times will be handled as follows:

- Adverse events with unknown start times, but with start date known, will be imputed with a time of 00:00, unless the start date corresponds to any given dosing date. In this case the start time will be imputed with the time of dosing. If this results in a start date/time after end date/time of the AE, then the time will also be imputed with 00:00.
- Adverse events with completely unknown start dates will be imputed with the date and time of dosing, unless the end date is known and prior to dosing; in that case the start date will be imputed as the date of Screening and a time of 00:00.
- Adverse events with partially known start dates/times will be treated as follows:
 - If only the day is missing, then the day will be imputed with the first day of the month, unless the month and year in which the AE started is a month and year in which IMP was administered, then the day will be imputed with the first day on which IMP was administered in that month. If this results in a start date after the end date, then the day will be imputed with the first day of the month.
 - If only the month is missing and the year is a year in which IMP was administered, then the month will be imputed with the first month in which IMP was administered. If this results in a start date after the end date of the AE, then the month will be imputed with JAN. If the known year part is not a year in which IMP was administered, then the month will also be imputed with JAN.
 - If both the day and month is missing and the year is a year in which IMP was administered, then the day and month will be imputed with the day and month of dosing. If this results in a start date after end date, then the day and month will be

imputed with 01JAN. If the year is not a year in which IMP was administered, then the day and month will also be imputed with 01JAN.

- If only the year is missing, then the year will be imputed with the year of dosing.

For purposes of the AE summaries, the following will apply:

- AEs with unknown intensity will be treated as "severe" for the tabulations.
- AEs with unknown relationship will be treated as "related" for the tabulations.
- AEs with unknown seriousness will be treated as "serious" for the tabulations.

There will be no imputation of AE data for the data listings. All data will be listed as recorded in the CRFs.

Adverse events with onset (start date/time) after dosing in Treatment Period 1, up to and including the final Follow-up visit will be summarised by treatment period and overall for all subjects, including tabulations by causality and severity (mild, moderate and severe). All tabulations will be presented by SOC and Preferred Term (PT). Furthermore, separate listings of SAEs, AEs that led to discontinuation (DAEs) and AEs that led to death will be presented.

Adverse events will be listed by subject and treatment, including the following information: verbatim term, SOC, PT and lowest level term, start date/time, end date/time, time from last dose, causality, action taken, whether the AE was classified as serious and the outcome.

All tabulations will include the number and percentage of subjects. In addition, a separate tabulation will be presented showing the number of events by treatment and PT.

Finally, an overview of all AEs will be presented, separately for the number and percentage of subjects and the number of events. This will include categories for any AE, AEs with outcome of death and SAEs

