3. STUDY DESIGN

3.1. Overall Study Design and Flow Chart

This study will be an open-label, 3-period, 3-treatment, fixed-sequence study in healthy subjects (males and females of non-childbearing potential), performed at a single Clinical Unit.

The study will comprise of the following periods (visits):

- A Screening Period of maximum 28 days (Visit 1);
- A fixed sequence of 3 Treatment Periods during which subjects will be resident at the Clinical Unit from one day prior to administration of verinurad+allopurinol (Day -1) of Treatment Period 1 until the morning of Day 5 of the Treatment Period 2, and similarly between Day -1 to Day 5 of Treatment Period 3. There will be a washout period of 14

days between Treatment Periods 2 and 3 dosing. The 3 Treatment Periods, including the washout period, will be a total of up to 36 days (Visits 2 to3);

• A Follow-up Visit within 7 to 14 days after the last administration of verinurad+allopurinol (Visit 4).

Subjects will be resident at the Clinical Unit from Day -1 of Treatment Period 1 (Visit 2), ie, prior to the evening meal the night before first dosing with verinurad+allopurinol, until the morning of Day 5 of Treatment Period 2, ie, at least 96 hours after the second dosing with verinurad+allopurinol. There will be no washout between Treatment Period 1 and Treatment Period 2. Subjects will be resident continuously for the full duration of Treatment Periods 1 and 2. There will be a minimum washout period of 14 days between dosing in Treatment Period 2 and dosing in Treatment Period 3. Subjects will not be required to be resident at the Clinical Unit for around 10 days during the washout period. Subjects will be resident again from Day -1 of Treatment Period 3 (Visit 3), ie, prior to the evening meal the night before third (last) dosing with verinurad+allopurinol, until the morning of Day 5 of Treatment Period 3, ie, at least 96 hours after the last dosing with verinurad+allopurinol. The subjects will return for a Follow-up Visit in 7-14 days after the last verinurad+allopurinol dose.

Each subject will receive a single dose of verinurad+allopurinol on 3 occasions, under fasted conditions. Each subject will also receive a single dose of cyclosporine on 1 occasion and a single dose of rifampicin on 1 occasion, with cyclosporine and rifampicin being dosed on separate occasions and always together with verinurad+allopurinol.

Details on IMP administration is provided in Section 5.4.3.

Figure 3-1 Study Flow Chart

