6.3.1. Adverse Events

6.3.1.1. Definition of Adverse Events

An AE is the development of any untoward medical occurrence in a subject or clinical study subject administered a medicinal product and which does not necessarily have a causal relationship with this treatment. An AE can therefore be any unfavorable and unintended sign (eg an abnormal laboratory finding), symptom (for example nausea, chest pain), or disease temporally associated with the use of a medicinal product, whether or not considered related to the medicinal product.

The term AE is used to include both serious and non-serious AEs and can include a deterioration of a pre-existing medical occurrence. An AE may occur at any time, including run-in or washout periods, even if no IMP has been administered.

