11.1.2. Safety Analysis Set

The safety analysis set will include all subjects who received at least the dose of verinurad+allopurinol in Treatment Period 1 and for whom any safety post-dose data are available.

Unless otherwise stated, the safety analysis set will be used for the presentation of all demographic and disposition data, as well as all safety analyses. Exposure to IMP will also be presented using the safety analysis set.

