11.2.5. Safety and Tolerability

All safety data (scheduled and unscheduled) will be presented in the data listings. Continuous variables will be summarised using descriptive statistics (n, mean, SD, minimum, median, maximum) by treatment. Categorical variables will be summarised in frequency tables (frequency and proportion) by treatment. The analysis of the safety variables will be based on the safety analysis set.

Adverse events will be summarised by PT and SOC using MedDRA vocabulary. Furthermore, listings of SAEs and adverse events that led to withdrawal will be made and the number of subjects who had any AE, SAEs, AEs that led to withdrawal, and AEs with severe intensity will be summarised. Adverse events that occur before dosing will be reported separately.

Tabulations and listings of data for vital signs, clinical laboratory tests and ECGs (listings only) will be presented. Any new or aggravated clinically relevant abnormal medical physical examination finding compared to the baseline assessment will be reported as an AE. Data will

be summarised for the observed values at each scheduled assessment, together with the corresponding changes from the baseline when baseline is defined. Clinical laboratory data will be reported in Système International units in the CSR.

Out-of-range values for safety laboratory will be flagged in individual listings as well as summarised descriptively using agreed standard reference ranges and/or extended reference ranges (eg, AZ, program, or laboratory ranges).

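### Adverse events are assigned to treatment by start time alone, with no rule for worsening after a later dose, and the denominator of by-treatment percentages is not stated

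*Combined protocol and SAP*

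**What the plan says.** Section 10.1.1 sets the attribution rule: "Adverse events will be assigned to a treatment based on the start date/time of the AE in relation to dosing in that treatment period". The Period 1 window covers "AEs with start date/time at the time of or after dosing in Treatment Period 1 until the time of dosing in Treatment Period 2", and the Period 2 window covers "AEs with start date/time at the time of or after dosing in Treatment Period 2 until the time of dosing in Treatment Period 3". The section has detailed rules for missing dates, but none for an AE that continues into a later period and then worsens.

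Section 6.3.1.4 lists what is collected for each AE, including start and stop date/time and intensity. It lists no date of intensity change. For serious AEs it adds the date on which the seriousness criteria were met.

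On timing, Section 3.1 states: "There will be no washout between Treatment Period 1 and Treatment Period 2". At least 14 days separate dosing in Periods 2 and 3. The sequence is fixed: verinurad+allopurinol alone, then with cyclosporine, then with rifampicin.

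On the population, Section 11.1.2 states: "The safety analysis set will include all subjects who received at least the dose of verinurad+allopurinol in Treatment Period 1". It also requires some post-dose safety data, but no dose in Period 2 or 3. Section 11.2.5 adds: "The analysis of the safety variables will be based on the safety analysis set", and "Categorical variables will be summarised in frequency tables (frequency and proportion) by treatment". Neither section says what the proportions are divided by. The only denominator written out, in Section 11.2.3.1, is all dosed subjects, and it is for demographic data.

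**The concern.** One secondary objective is the safety and tolerability of verinurad and allopurinol when given with cyclosporine or rifampicin. The by-treatment AE tables, including those by severity, are the main summary of it. Under a start-only rule, a worsening after the interacting drug can stay in the column of the preceding treatment. The first transition is the most exposed, because an AE from Period 1 can still be present when cyclosporine is given.

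The situation is plausible on the protocol's own account. Section 3.3.1 names headache as the most common AE with verinurad, and Section 3.3.3 lists headache among the cyclosporine side effects.

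The denominator raises a second, independent question. Rifampicin always comes last, so any dropout falls on its column. Section 11.2.1 says that no separate SAP will be written, so the protocol is where both rules need to stand.

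**Working it through.** The plan gives no by-treatment AE rate or denominator, so there is no figure of its own to reproduce. The only numbers needed are 14 enrolled and at least 12 evaluable at the end of the last period (Section 11.4).

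**Attribution.** Take one subject with a mild headache that starts late in Period 1, is still present at the cyclosporine dose and then becomes severe. Suppose all 14 subjects are dosed in both periods, and that a single record carries the highest intensity.

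| How the site records it | Severe, verinurad+allopurinol | Severe, + cyclosporine | Any AE, verinurad+allopurinol | Any AE, + cyclosporine |
|---|---|---|---|---|
| One record, start in Period 1 | 1/14 = 7.1% | 0 | 1/14 = 7.1% | 0 |
| New record at worsening | 0 | 1/14 = 7.1% | 1/14 = 7.1% | 1/14 = 7.1% |

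In the severe row, the difference (cyclosporine minus reference) changes from −7.1 to +7.1 percentage points, a swing of 2/14 = 14.3 points from one subject. If the single record instead kept the initial intensity, the worsening would appear in no column.

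For an AE that starts in Period 2 and worsens after rifampicin, the same rule gives cyclosporine, which is a combination column and not the reference. The interval of at least 14 days makes this less likely.

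**Can it be recovered later?** The AE listing described in Section 10.1.1 names start, end, time from last dose, causality, action taken, seriousness and outcome. It does not name intensity. Even if intensity is listed, the variables in Section 6.3.1.4 hold no time at which it changed. Seriousness is different, because its date is collected.

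**Denominator.** For 3 affected subjects in the rifampicin column:

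- 14 dosed in Period 3: 3/14 = 21.4%, so the two denominators agree
- 13 dosed: 3/13 = 23.1%
- 12 dosed: 3/12 = 25.0%
- 10 dosed: 3/10 = 30.0%

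If the whole safety set of 14 is used when 12 were dosed, the reported percentage is 12/14 = 0.857 of the percentage among those exposed. The cyclosporine column is affected in the same way if a subject leaves after Period 1.

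**The case against.** The strongest reply is that the protocol already treats worsening as an AE. Section 6.3.1.1 says an AE "can include a deterioration of a pre-existing medical occurrence". Section 6.3.4.1 requires a clinically relevant worsening of an ECG finding to be recorded, and Sections 6.3.1.4 and 10.1.3 do the same for physical examination findings aggravated since baseline. A worsening entered as its own AE has a later start and goes to the later treatment. This stands to the extent that misassignment depends on how the site records the event. It does not close the gap. The definition permits a new record but does not instruct the site to open one. ECGs are scheduled only at Screening and Follow-up. The examination rule compares with baseline, not with the preceding period.

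On the denominator, Sections 11.1.2 and 11.2.5 name a population and do not fix a column total. Using subjects dosed in each period would be consistent with the text. That stands: the denominator is unstated, not wrong.

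A reader might also infer that both gaps consistently make the combinations look safer than the reference. The documents do not support that. Worsening after rifampicin would count under cyclosporine. The Period 2 window lasts at least 14 days against Days 1 to 5 for Period 1, so late-onset events also accumulate under cyclosporine. The net direction is not established.

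Finally, the impact is limited: these are descriptive tables in a small open-label study, and the primary pharmacokinetic analysis does not use them.

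**Conclusion.** The point holds as a conditional gap in the descriptive safety tables. If an AE from one period worsens after the next dose and the site keeps one record, its higher intensity can be tabulated under the earlier treatment, and the collected data cannot show when the change happened. In the severe row, one such subject can swing the cyclosporine-minus-reference difference by 14.3 points, assuming 14 dosed in both periods and the highest intensity kept.

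How often this would happen cannot be estimated from the documents. A reader might scale the pooled 29.4% AE rate in Section 3.3.1 to 14 subjects (14 × 0.294 = 4.1) and read off a probability of misassignment. That rate covers eight whole studies over a range of doses, not one single-dose period. The share of AEs still present at the next dose is not given, and an ongoing AE is not a worsening one.

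The denominator part is missing detail. It would be wrong to conclude that the rifampicin percentages will be diluted; they would be only if the whole safety set were used and some subjects did not reach Period 3. The 21.4% against 25.0% rests on an assumed 12 of 14 dosed. The 12 in Section 11.4 is the minimum number evaluable, and a subject can be dosed with rifampicin yet have pharmacokinetic data excluded under Section 11.1.3.

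**What to change.** Three additions:

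- **Section 6.3.1.4:** an AE that increases in intensity after a later dose is recorded as a new AE, with its start at the date/time of worsening. An AE that becomes serious keeps its existing record and the date already collected for meeting the seriousness criteria, which can be used for assignment.
- **Section 10.1.1:** assign AEs by date/time of start or of worsening. The seriousness date is listed without a time, so the section's existing convention for a known date that falls on a dosing day can be reused.
- **Section 11.2.5:** by-treatment percentages use the safety-set subjects dosed in that Treatment Period.

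The cost is a few sentences, one CRF completion instruction and a change to the table code. The downside is small: a worsened AE counts twice in the event-count table, which a footnote can explain.
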